Purpose of clinical study	To use whole-genome sequencing to investigate the colonisation and transmission of multidrug- resistant organisms in the adult intensive care unit at Addenbrooke's Hospital		
Primary objective	To determine the rates of carriage, infection and transmission of multidrug-resistant Gram- negative organisms in the adult intensive care unit at Addenbrooke's Hospital using bacterial whole-genome sequencing.		
Secondary objective (s)	 To compare standard epidemiological investigation / typing with whole-genome sequencing in the investigation of suspected outbreaks To conduct a health economic evaluation of standard epidemiological investigation / typing with whole-genome sequencing in the surveillance and investigation of suspected outbreaks and the management of confirmed outbreaks 		
Study Design	Observational cohort study of all patients admitted to the adult intensive care unit at Addenbrooke's hospital during the study period		
Primary Outcome Measures	 Number of patients colonised with multidrug-resistant organisms Number of patients with clinical evidence of infection with multidrug-resistant organisms Number of transmission events of multidrug-resistant organisms 		
Secondary Outcome Measures	 Risk factors for colonisation / infection with multidrug-resistant organisms Outcome of patients colonised / infected with multidrug-resistant organisms Cost-consequences of whole-genome sequencing versus standard epidemiological investigation / typing for surveillance and investigation of suspected outbreaks and the management of confirmed outbreaks 		
Sample Size	600 patients		
Summary of eligibility criteria	 Inclusion Criteria: Adult (age 18 years older) Male or Female Admitted to adult intensive care Exclusion Criteria Age <18 years Does not fulfil study inclusion criteria 		

Screening & enrolment	Participants will be screened for carriage of multidrug-resistant organisms on admission to the adult intensive care unit and enrolled into the study. Written informed consent will not be required prior to study enrolment as this is a surveillance study for healthcare-associated infections. Clinical and antibiotic treatment data will be collected at enrolment	
Treatment period	Participants will undergo screening for multidrug-resistant organisms on admission, discharge and weekly throughout their admission to ICU. Clinical data and microbiological specimens will be collected on admission to ICU, on discharge from ICU and weekly during the ICU admission period for patients admitted for 7 days or more.	
End of Study	The end of the study will be the date that specimen and data collection are completed	
Procedures for safety monitoring during study	Not applicable, as this is an observational cohort study and not an intervention study	
Criteria for withdrawal of patients	Not applicable, as this is an observational cohort study and not an intervention study	

6 Study Flow Chart

7 Background

The emergence and spread of antimicrobial resistance (AMR) poses a significant challenge to the safe delivery of modern medical care. Indeed AMR has been identified as a major threat to human health by the Chief Medical Officer (1), and has resulted in the development of a five-year Antimicrobial Resistance Strategy Plan by the Government to address this threat (2).

Multidrug-resistant organisms (MDRO) are found more commonly in healthcare settings where they contribute to the burden of healthcare-associated infections (HCAI). In 2011 the estimated prevalence of HCAI was 6.4% (95% confidence interval 4.7 to 8.7%) with the highest prevalence (24.7%) in intensive care units (3). Over the past 15 years considerable efforts have been made to reduce the burden of HCAI in the United Kingdom (UK). These have included screening and decolonisation of patients with methicillin-resistant *Staphyloccocus aureus* (MRSA) (4), and mandatory reporting of MRSA bacteraemia (5) and *Clostridium difficile* infection (CDI) (6). These have resulted in dramatic reductions in MRSA bacteraemia and CDI (3). However, new threats such as vancomycin-resistant enterococci (VRE) (7) and multidrug-resistant Gram-negative bacilli (MDR GNB) have emerged (8). In particular the emergence and spread of resistance to carbapenem drugs, considered to be last-line agents, is a great concern (9). In response to this, Public Health England has recently published a toolkit to enable acute hospital trusts to identify and manage patients who are colonised or infected with carbapenem-resistant Enterobacteriaceae (CRE) (10).

Patients in intensive care units are particularly vulnerable to HCAI as they are critically ill (often with multiorgan failure), have multiple invasive medical devices (e.g. intravascular lines, urinary catheters, mechanical ventilation) and are frequently treated with broad-spectrum antibiotics (which select antibiotic-resistant organisms). Several outbreaks of infection caused by MDROs in intensive care units have been reported (11). They are often recognised late, and are associated with high mortality. Methods to prevent HCAI and improve early detection of MDRO outbreaks in this population are urgently required.

When a suspected outbreak is identified samples are collected from the index patient as well as other patients who may have been affected and, occasionally, from medical staff. Current methods to determine the relatedness of bacterial isolates rely on molecular typing which is often performed in reference laboratories (rather than local laboratories) and take too long to inform outbreak management in real time. Indeed in most cases the results may only be available 1 to 2 weeks later and are used retrospectively to confirm or refute the outbreak.

Microbial whole-genome sequencing (WGS) is an emerging technology that will transform the practice of clinical microbiology (12). It is now possible to sequence a microbial genome in one day and obtain information about organism identity, antimicrobial resistance, genotype, genetic relatedness and virulence determinants (13). This single technology could, therefore, replace several processes that currently occur in diagnostic and reference laboratories. The information produced can be applied to clinical practice in a number of ways. First, it can enhance the epidemiological investigation of suspected outbreaks and inform infection control and public health interventions. Second, it can guide the management of patients with highly drug-resistant organisms, for example multidrugresistant and extensively drug-resistant tuberculosis. Third, it can be used for the detection and surveillance of antimicrobial resistance, including during the evaluation and use of new antimicrobial agents.

We have previously conducted one of the first studies to demonstrate the potential utility of WGS in nosocomial outbreak investigation at Addenbrooke's Hospital (14). In this study we retrospectively investigated an MRSA outbreak in a neonatal intensive care unit by sequencing MRSA isolates from infants on the unit and from control patients located elsewhere in the hospital. Bacterial sequence data analysis revealed a cluster of outbreak

strains that were clearly separated from the control isolates; we also detected a previously unsuspected transmission event between two of the control patients. In a second study we applied WGS during the course of suspected ongoing MRSA outbreak in Special Care Baby Unit (15). In this study, we sequenced MRSA isolates from infants who were admitted to the special care baby unit (SCBU) at Addenbrooke's hospital over a six-month period. These were found to be a novel MRSA strain (ST2371). Sequencing of additional MRSA isolates with the same antibiotic susceptibility profile identified 24 cases that were epidemiologically linked, indicating spread between infants on the SCBU, mothers on the post-natal ward, and family members in the community. A new case, which occurred 64 days after the previous case, prompted screening of healthcare workers on the unit. One person was found to be carrying the outbreak strain, and no further cases were detected after they were successfully decolonized. This study demonstrated for the first time the ability to use bacterial WGS in real-time to successfully manage an outbreak.

Klebsiella pneumoniae is an important nosocomial pathogen in intensive care units, particularly among immunocompromised patients. In recent years *K. pneumoniae* strains resistant to carbapenems have emerged and spread worldwide. In 2011, the United States National Institutes of Health experienced an outbreak of carbapenem-resistant *K. pneumoniae* that affected 18 patients, 11 of whom died (16). Snitkin and colleagues sequenced *K. pneumoniae* isolates from the affected patients and found that the outbreak was monoclonal despite a three-week gap between the index case and subsequent cases. They identified at least three independent transmission events from the index case, resulting in two major clusters of colonized patients. One patient could be linked to a contaminated ventilator. They also identified putative resistance mutations is isolates that had become resistant to colistin.

A number of other studies have used WGS to investigate nosocomial outbreaks caused by a variety of pathogens including multidrug-resistant *Acinetobacter baumannii* (17), vancomycin-resistant *Enterococcus faecium* (18, 19), carbapenem-resistant *Enterobacter cloacae* (18), and *Pseudomonas aeruginosa* (20). Of note, most of these studies were conducted retrospectively and did not influence individual patient management, or the course of the outbreak.

8 Rationale for Study

One strategy to reduce HCAI in the ICU setting would be to perform prospective surveillance for MDRO in patients admitted to critical care units in order to identify them more quickly and to enable the earlier implementation of appropriate infection control measures and tailored antimicrobial therapy. Current practices for screening for MDRO vary between countries, hospitals and units, reflecting a lack of data and the uncertainty around best practice.

We do not currently perform surveillance for MDRO at Addenbrooke's Hospital, apart from screening patients who fulfil the criteria for CRE screening outlined in the PHE recommendations above (10). We therefore do not have accurate data on the prevalence of these organisms in our hospital, as we rely on samples taken for clinical diagnostic purposes. Furthermore we are unlikely to be able to detect transmission of these organisms between patients as they only come to attention if more than one patient in the same ward develops an infection with the same organism at the same time.

In terms of microbiological data from clinical specimens the prevalence of MRSA colonisation and *C. difficile* infection in the ICU is low at 2.9% and 4% respectively. For blood cultures the frequency of positive cultures is 17% and the most commonly isolated bacteria are *Enterococcus faecium*, coagulase-negative staphylococci, *Elizabethkingia meningoseptica, E. coli, Klebsiella pneumoniae, Pseudomonas aeruginosa, Stenotrophomonas maltophilia* and *Staphylococcus aureus*. In terms of respiratory samples (sputum, tracheal aspirate, broncho-alveolar lavage) the frequency of positive cultures is 57%, and the most commonly isolated bacteria are *P. aeruginosa, Stenotrophomonas maltophilia, S. aureus, Elizabethkingia meningoseptica, E. coli, K. pneumoniae* and *Enterobacter* spp. In terms of urine samples the frequency of positive cultures is 20.3%, and the most commonly isolated bacteria are *E. coli, K. pneumoniae, E. faecium, P. aeruginosa, Proteus spp, and E. cloacae.*

There are previously published studies on whole-genome sequencing of MRSA prevalence and transmission in an ICU setting (21), and of *C. difficile* prevalence and transmission in a hospital setting (22). We have therefore decided to focus our study on vancomycin-resistant enterococci (VRE) and multidrug-resistant Gram-negative bacilli (MDR GNB) e.g. (*Escherichia coli, Klebsiella pneumoniae, Enterobacter spp, Acinetobacter spp, Pseudomomas aeruginosa and Elizabethkingia meningoseptica*) as they are known to spread readily in an ICU setting, but their prevalence and rates of transmission are unknown. Furthermore they can be very difficult to treat because of the limited number of effective antibiotics available to treat them.

In order to address these limitations, we propose to conduct a prospective surveillance study of MDRO in adults admitted to the John Farman Intensive Care Unit at Addenbrooke's hospital in Cambridge. This will enable us to determine the rates of carriage and infection in this vulnerable patient population, and to identify possible intervention and control strategies. We will compare standard epidemiological investigation / typing methods with WGS to determine transmission of MDRO between patients on the ICU to determine whether WGS is more sensitive than current standard methods of detection MDRO. We will also conduct a parallel health economic evaluation to determine the cost-effectiveness of this strategy.

9 Study design

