11.2 Baseline assessments

11.2.1 Screening for multidrug-resistant organisms (research specimens)

Participants will be screened for MDRO on admission to the John Farman Intensive Care Unit. All specimens will be assigned a unique anonymised identification number prior to transfer to the research laboratory the Department of Medicine for processing.

Specimens will be cultured on selective media for the following target organisms:

- Vancomycin-resistant enterococci (VRE)
- Extended spectrum beta-lactamase producing Enterobacteriaceae (ESBL)
- Carbapenem-resistant organisms (CRO)

Samples that are positive for suspected target organisms will undergo identification using MALDI TOF MS and antimicrobial susceptibility testing using the Vitek-2 system.

Isolates that are confirmed to be target organisms will undergo DNA extraction and storage at -80 $^\circ\text{C}.$

DNA extracts will be transferred in batches to the Wellcome Trust Sanger Institute for DNA library preparation and high-throughput microbial whole-genome sequencing.

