13.1 Primary outcome measures

The primary outcome measures are:

- Number of patients colonised with MDRO during the study period
- Number of patients with clinical evidence of infection with MDRO during the study period
- Number of transmission events of MDRO, detected by the current infection control procedures and by analysis of whole genome sequence data during the study period.

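### The primary contrast between WGS and current infection control procedures changes sampling and typing method together, so a higher WGS count cannot be credited to WGS itself

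*Protocol*

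**What the plan says.** **Aim.** Section 8 (Rationale) says the two approaches will be compared "to determine whether WGS is more sensitive than current standard methods of detection MDRO".

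**Outcome.** Section 13.1 lists as a primary outcome: "Number of transmission events of MDRO, detected by the current infection control procedures and by analysis of whole genome sequence data".

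**What current practice sees.** Section 8 says of local prevalence data that "we rely on samples taken for clinical diagnostic purposes". It states one exception to the absence of surveillance: "apart from screening patients who fulfil the criteria for CRE screening outlined in the PHE recommendations above". On transmission, it says of these organisms that "they only come to attention if more than one patient in the same ward develops an infection with the same organism at the same time". Section 7 (Background) adds that a suspected outbreak prompts sampling of the index patient, other possibly affected patients and occasionally staff.

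**What WGS sees.** Every participant is screened on admission and discharge, and weekly if the stay is 7 days or longer (sections 11.2.1, 11.3.1 and 11.5.1). Section 11.2.1 continues: "Isolates that are confirmed to be target organisms will undergo DNA extraction and storage", after which the DNA goes for sequencing. Target-positive diagnostic samples are retrieved for the same processing (sections 11.2.2 and 11.3.2).

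**Non-WGS data on the same isolates.** Screening positives have MALDI-TOF identification and Vitek-2 susceptibility testing. Section 15.1 mentions, in one sentence, transmission rates from epidemiological and microbiological data.

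**Secondary comparison.** Section 9.5.2 compares conventional investigation and typing with WGS within suspected outbreaks.

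**The concern.** Sensitivity is a property of a method applied to given material. Here the material differs between the two sides. One side is a routine system that draws mainly on clinical samples and is alerted by concurrent infections. The other is systematic screening of every patient followed by sequencing. If WGS yields more transmission events, the excess may come from finding more carriers, from linking isolates better, or from both, and the 13.1 contrast cannot separate these.

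Sensitivity also needs a denominator of true transmission events, and the protocol names none that is independent of WGS.

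What is at stake is the interpretation of a primary outcome. The study could report that WGS outperforms current methods when the gain came largely from universal screening. A unit deciding whether to fund screening, sequencing or both would then be misinformed.

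**Working it through.** **1. The plan's own figure.** The only relevant planning figure is 600 patients: 1200 admissions per year × 0.5 = 600. The lower end of the range in section 15.1 gives 1100 × 0.5 = 550. This is a feasibility number, and the point does not depend on it.

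**2. The two sides compared.**

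| | Current procedures | WGS |
|---|---|---|
| Main sample base | Clinical diagnostic samples (section 8) | Universal screening plus diagnostic isolates (11.2, 11.3) |
| Additional samples | Targeted CRE screening (section 8); outbreak sampling (section 7) | None needed |
| Trigger | Concurrent same-organism infections (section 8) | None; all confirmed target isolates |
| Linking method | Conventional investigation and typing | Phylogenetic relatedness (15.2) |

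Every row differs. A pure method comparison would differ only in the last.

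**3. Illustration of size.** The documents give no figure for how many carriers current procedures can see, so the inputs here are assumptions:

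- f = fraction of carriers visible to current procedures.
- WGS sees all carriers.
- s = probability of correctly linking a true pair when both isolates are in hand, equal for the two methods.

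WGS detects a share s of true pairs. Current procedures detect s × P(both members visible). That probability is f² if visibility is independent within a pair and f if it is perfectly correlated. The apparent ratio of WGS to current is therefore 1/f² or 1/f, and s cancels.

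| f | Perfect correlation, 1/f | Independence, 1/f² |
|---|---|---|
| 0.5 | 2 | 1/0.25 = 4 |
| 0.2 | 5 | 1/0.04 = 25 |
| 1.0 (same isolates) | 1 | 1 |

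The true ratio of methods is 1 in every row.

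**4. With a real method difference.** Suppose, again as an assumption, that the linking probabilities on the same isolates are 0.95 for WGS and 0.75 for conventional methods. The like-for-like ratio is 0.95/0.75 = 1.27. Under independence, the 13.1 contrast would show 0.95/(0.75 × 0.25) = 5.07 at f = 0.5 and 0.95/(0.75 × 0.04) = 31.7 at f = 0.2. On the same isolates (f = 1) it returns 1.27.

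**The case against.** **Current procedures are not confined to clinical samples.** A reader might infer that they are. Section 8 excepts targeted CRE screening, carbapenem-resistant organisms are one of the three target groups, and section 7 describes further sampling in a suspected outbreak. This stands. It narrows the gap between the two sides without closing it.

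**Nothing says screening results are withheld from infection control.** Section 11.5.2 mentions release to ICU staff for diagnostic specimens only, the protocol is silent on research screens, and the flow chart is not in the text available. That also stands: separation is inferred. If results were shared, though, the comparator would no longer be current practice, so the protocol needs to say which applies.

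**Section 15.1 already plans a non-WGS transmission analysis.** Its sentence on epidemiological and microbiological data could be read that way. It names no isolate set or rule and is not tied to the 13.1 contrast, which still names current infection control procedures as the comparator.

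**The details belong in the SAP.** Linkage rules and agreement tables often do. The choice of comparator and the sensitivity aim are fixed in the protocol, and those are what is at issue.

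**The wider aims are not invalidated.** The primary objective is descriptive, and the sensitivity wording appears only in the rationale. The secondary comparison can use the same isolates inside a suspected outbreak. The economic outcome in sections 9.6.2 and 13.2 is also limited to suspected outbreaks; only the synopsis adds surveillance. All of this stands, so the documents do not support a claim that the secondary objective or the economic evaluation simply inherits the 13.1 contrast.

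**The illustration ignores false links.** Conventional rules may over-call links that WGS refutes, which would raise the current count. This is correct, and it is a further reason why a ratio of counts is not a measure of sensitivity.

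**Conclusion.** The concern holds for the 13.1 contrast read with the aim in section 8. Sampling and typing method change together, so a higher WGS count cannot be attributed to WGS, and there is no independent reference against which to call either approach sensitive. This follows from the text and needs no assumed number.

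The size is unknown. The ratios of 2 to 4 at f = 0.5 and 5 to 25 at f = 0.2 show what unequal sampling alone could produce with equally accurate methods. They rest on an assumed f, on WGS seeing all carriers, on visibility within a pair lying between independent and perfectly correlated, and on no false links. They should not be read as estimates for this unit.

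A reader might also infer that WGS is 100% sensitive by construction. That would be so only if WGS defined the true events, and the protocol does not say that it does.

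Secondary objective 1 is less affected. However, suspected outbreaks are identified by current procedures, so results from that subset cannot support an overall sensitivity claim.

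**What to change.** In sections 13.1 and 15.1:

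1. Make the method comparison on one isolate set. Apply a fixed non-WGS rule (same species, same Vitek-2 antibiogram, overlapping or sequential ICU stay) to all study isolates, blind to WGS. Compare it with WGS by paired agreement on patient pairs: linked by both, by WGS only, by the standard rule only.
2. Report the gain from screening separately, as WGS on all isolates against WGS on diagnostic isolates only.
3. Present current procedures as run only as a description of the whole strategy. Setting them against WGS on clinical isolates would still mix the alert trigger with the typing method, so it should not be labelled a method effect.
4. State whether screening results reach the infection control team during the study.

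In section 8, replace the sensitivity wording with agreement and additional links detected, or reword the aim as screening plus WGS against current practice.

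**Cost.** Changes of wording and some extra analysis. Identification and Vitek-2 results are already planned, so the antibiogram-based rule needs no new laboratory work. It uses ICU stay because the protocol does not expressly say that bed location is recorded. The headline contrast is likely to be less favourable to WGS.

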9.1 Statement of design

This a surveillance study of MDRO and there are no study-specific treatments or interventions. The study design is a prospective observational cohort study of all adults admitted to the John Farman ICU during the six-month study period. Patients will be screened for MDRO on admission to ICU, on discharge from ICU, and weekly during their ICU admission period if the duration of admission is 7 days or longer. Participants will receive routine standard clinical care, including antibiotics to treat infections as clinically indicated.

